4.2.2. Secondary Endpoints

The secondary endpoints are:

Efficacy:

- Proportion of patients achieving EASI-50, EASI-75, and EASI-90 ($\geq 50\%$, $\geq 75\%$, and $\geq 90\%$ improvement from baseline) at week 16
- Absolute change in EASI scores from baseline to week 16
- Proportion of patients with both an IGA score of 0 or 1 (on a 5-point scale) and a reduction from baseline of ≥ 2 points at week 16
- Change (absolute and percent) from baseline to week 16 in weekly average of daily peak Pruritus Numerical Rating Scale (NRS)
- Proportion of patients with improvement (reduction) of weekly average of daily peak Pruritus NRS ≥ 4 from baseline to week 16
- Time to onset of effect on pruritus during the 16-week treatment period (≥ 4 -point reduction of weekly average of daily peak Pruritus NRS from baseline)
- Percent change from baseline to week 16 in SCORing Atopic Dermatitis (SCORAD)
- Change from baseline to week 16 in percent BSA of AD involvement

Safety:

- Incidence of treatment-emergent adverse events (TEAEs) from baseline through end of treatment (week 16)
- Incidence of treatment-emergent serious adverse events (SAEs) from baseline through end of treatment (week 16)
- Incidence of treatment-emergent adverse events of special interest (AESIs) from baseline through end of treatment (week 16)
- Incidence of TEAEs from baseline through end of study (week 36)
- Incidence of treatment-emergent SAEs from baseline through end of study (week 36)
- Incidence of treatment-emergent AESIs from baseline through end of study (week 36)

Pharmacokinetic:

- Concentrations of functional REGN3500 in serum by treatment regimen at each assessment timepoint from baseline to end of study (week 36)

Any exploratory endpoints will be described in the statistical analysis plan (SAP).

Note: The safety and PK endpoints will not be included in the testing hierarchy.

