8.1.2. Early Termination Visit

Patients who permanently discontinue study drug but who do not withdraw from the study will be asked to return to the clinic for all remaining study visits per the visit schedule (see Section 7.4.2 and Table 2). Patients who are withdrawn from the study will be asked to return to the clinic for ET assessments, only (Table 2).

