9.4.2. Serious Adverse Events

All SAEs, regardless of assessment of causal relationship to study drug, must be reported to the sponsor (or designee) within 24 hours. Refer to the study reference manual/site binder or file for the procedure to be followed.

Information not available at the time of the initial report must be documented in a follow-up report. Substantiating data such as relevant hospital or medical records and diagnostic test reports may also be requested.

In the event the investigator is informed of an SAE after the patient completes the study, the following will apply:

- SAE with an onset within 30 days of the EOS visit or within 140 days of last study drug administration if the patient early terminated from the study - the SAE will be reported to the sponsor. The investigator should make every effort to obtain follow-up information on the outcome until the event is considered chronic and/or stable.
- SAE with an onset day greater than 30 days from the EOS/ET visit - only fatal SAEs and those deemed by the investigator to be drug-related SAEs will be reported to the sponsor. The investigator should make every effort to obtain follow-up information on the outcome of a drug-related SAE until the event is considered chronic and/or stable.

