3.2. The Safety Analysis Set (SAF)

The safety analysis set (SAF) includes all randomized patients who received any study drug; it is based on the treatment received (as treated). Treatment compliance/administration and all clinical safety variables will be analyzed using the SAF.

The actual treatment group as treated is defined by the following rules:

- For a patient randomized to receive REGN3500, if the patient received all placebo injections, the actual treatment will be assigned as placebo.
- For a patient randomized to receive REGN3500, if the patient received at least one REGN3500 injection as planned, the actual treatment will be same as the planned treatment.
- For patients randomized to receive matching placebo for REGN3500 but accidentally received REGN3500 once injection, the actual treatment will be assigned as REGN3500.

The safety analysis will be performed separately for the treatment period, follow-up period and overall study period as defined below.

Treatment period: from the date of the first dose of study drug to the date of the end of treatment which is defined as:

- the date of Week 16 visit (or study day 113 starting from the first dose of study drug if the date of the Week 16 visit is unavailable for those patients who completed the 16 week)
- the date of early termination visit, for those patients who did not complete the Week 16 visit
- 12Feb2020 for the patients who were early terminated from the treatment per Sponsor's decision to stop the study on 12Feb2020 and Week 16 visit or early termination visit is unavailable.

Follow-up period: from the date of the end of the treatment to the date of the end of study visit

Overall study period: from the date of the first dose of study drug to the date of the end of study visit

For the analyses of follow-up period, only a subset of SAF will be included, which is defined as the patients who entered the follow-up period and had at least one visit during the follow-up period.

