5.8.1. Adverse Events

Listing of TEAEs, serious TEAEs, and TEAEs resulting in death and study drug discontinuation will be generated.

Numbers and proportions of patients reporting TEAEs will be summarized for treatment period and follow-up period, sorted by alphabetical order of SOC and decreasing frequency of PT based on the incidence in the REGN3500 treatment group.

Summaries of TEAEs will include:

- TEAEs
 - TEAEs by SOC/PT
 - TEAEs by SOC/HLT/PT
 - TEAEs by PT
 - Common TEAEs by SOC/PT (incidence with PT $\geq 5\%$)
 - TEAEs related to study drug as assessed by the investigator by SOC/PT
 - TEAEs related to study procedure as assessed by the investigator by SOC/PT
 - TEAEs by severity by SOC/PT
 - Severe TEAEs by SOC/PT
 - Severe TEAEs related to study drug as assessed by the investigator by SOC/PT
 - Severe TEAEs related to study procedure as assessed by the investigator by SOC/PT
 - Common non-serious TEAEs by SOC/PT (incidence with PT $\geq 5\%$)
 - TEAE per 100 patient years by SOC/PT during treatment period only
- Serious TEAEs by SOC/PT
 - Serious TEAEs by SOC/PT
 - Serious TEAEs by SOC/HLT/PT
 - Serious TEAEs related to study drug as assessed by the investigator by SOC/PT
 - Serious TEAEs related to study drug as assessed by the investigator by SOC/PT
- TEAEs leading to permanent discontinuation from study treatment by SOC/PT
- Serious TEAE per 100 patient years by SOC/PT during treatment period only
- Death by SOC/PT

- Skin infection TEAEs by SOC and PT

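### The visit condition on the follow-up safety subset (SAP 3.2) can leave a death or SAE out of both period tables, and SAP 5.8.1 does not name the overall-period table that would catch it

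*SAP*

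**What the plan says.** **Periods and subset (SAP 3.2).** The section states: "The safety analysis will be performed separately for the treatment period, follow-up period and overall study period as defined below".

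- The treatment period ends at the Week 16 visit, or at day 113 for a completer whose visit date is missing. Otherwise it ends at "the date of early termination visit, for those patients who did not complete the Week 16 visit". For sponsor-stopped patients with neither visit it ends on 12 February 2020.
- The follow-up period runs from that date to the end-of-study (EOS) visit. Its analyses use a subset of the safety analysis set (SAF): "the patients who entered the follow-up period and had at least one visit during the follow-up period".
- The third period is defined as "Overall study period: from the date of the first dose of study drug to the date of the end of study visit". The subset rule is not applied to it.
- No end date is given for a patient who never has an EOS visit.

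**Adverse event tables (SAP 5.8.1).** "Numbers and proportions of patients reporting TEAEs will be summarized for treatment period and follow-up period". The overall period is not mentioned there. SAP 5.8.3 to 5.8.5 (laboratory, vital signs, ECG) do mention it. SAP 5.8.1 also plans listings of TEAEs, serious TEAEs and fatal TEAEs, with no visit condition, and a table of deaths.

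**Protocol.**

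- Section 8.1.2: "Patients who are withdrawn from the study will be asked to return to the clinic for ET assessments, only".
- Section 9.4.2 still has SAEs reported to the sponsor when onset is "within 140 days of last study drug administration if the patient early terminated from the study".
- Section 9.4.6 collects adverse event information only up to the last study visit.
- Section 10.4.4.1 defines the periods by date, with no attendance condition, and asks for TEAE summaries over the whole treatment-emergent period as well as each part.
- Section 4.2.2 counts the week-36 TEAE, SAE and AESI endpoints from baseline.

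**The concern.** Whether a patient belongs to the follow-up subset is decided after treatment, by an attendance that the outcome itself can prevent. A patient who dies before the first follow-up visit cannot qualify. A patient who leaves at an ET visit has no later scheduled visit, yet the protocol goes on requiring SAE reports. In both cases the treatment period is already closed, so the event has no period table to fall into.

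After the early stop, SAP 1.2.4 says enrolled patients were moved into follow-up for safety assessments, so serious events in that phase are among the main things the abbreviated report can still deliver. SAP 1.2.4 lists the departures from the protocol's statistical section, and the visit condition is not among them.

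**Working it through.** The plan gives no figure on this point to reproduce, so the check is a trace through the rules followed by simple arithmetic.

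**1. Where does a serious event go?**

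| Patient | Treatment-period table | Follow-up table |
|---|---|---|
| End-of-treatment visit done, dies before any later visit | No: onset is after the period end | No: no follow-up visit |
| Leaves at an ET visit before week 16, SAE later reported under protocol 9.4.2 | No: period ended at the ET visit | No: no later visit, and arguably never entered follow-up |
| Sponsor-stopped with neither Week 16 nor ET visit, no later visit, SAE reported | No: period ended 12 February 2020 | No: no follow-up visit |
| Hospitalised after end of treatment, later seen at any scheduled or unscheduled visit | No | Yes, on a plain reading |

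The first three rows are lost from both numerator and denominator of the follow-up table. The fourth is not lost: one later visit is enough, and SAP 6.4 maps unscheduled visits after treatment end, and ET visits during follow-up, to follow-up visits.

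**2. How long is the exposed interval for a patient who enters follow-up?** From the schedule of events, end of treatment is day 113, the first follow-up visit day 141, and end of study day 253.

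- Before the first follow-up visit: 141 − 113 = 28 days.
- Whole follow-up: 253 − 113 = 140 days.
- Share: 28/140 = 20%. With the +3-day visit window, 31/140 = 22%.

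SAP 6.4 uses the same 28 and 140 days as target days relative to the treatment-period end, so this also applies to sponsor-stopped patients. For a patient who left at an ET visit the exposed interval is all the later SAE reporting time.

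**3. Does the overall-period analysis catch these events?** SAP 3.2 says there is one, on the SAF without the subset rule. SAP 5.8.1, where the adverse event tables are specified, names two periods, while the three sections that follow name three. Protocol 10.4.4.1 names the whole treatment-emergent period explicitly. So the general statement in SAP 3.2 covers these events, but the section a programmer would build the tables from does not. The overall period also closes at an EOS visit that these patients never have.

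**4. What is one event worth?** SAP 2.2 gives 129 randomised patients in 5 arms: 129/5 = 25.8 per arm. Assume 26 treated per arm.

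- One SAE, in a patient with no follow-up visit: the follow-up table shows 0%, against 1/26 = 3.8% on the full SAF.
- Two SAEs, one of them in such a patient, with 1 to 5 non-attenders: 1/25 = 4.0% to 1/21 = 4.8%, against 2/26 = 7.7%.
- One SAE in an attender and 5 event-free non-attenders: 1/21 = 4.8%, against 1/26 = 3.8%. Here the restriction raises the rate.

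**The case against.** A reader might infer that the week-36 safety objective is answered only for patients who attend follow-up, or that late incidence is biased downward. The documents support neither.

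- The week-36 endpoints run from baseline, SAP 3.2 plans an overall-period analysis without the visit condition, and serious and fatal TEAEs are listed regardless of attendance.
- Missing the week 20 visit does not exclude anyone who attends later. Exclusion needs death, or no visit at all, after the treatment-period end.
- The direction of bias depends on who fails to attend, as the last line of the arithmetic shows, and the documents do not tell us.

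Three further points on the other side have force.

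- For patients who leave at an ET visit, the visit clause is only part of the problem. They may not count as having entered follow-up, and the period ends at an EOS visit they never have. The protocol shares that end point, so deleting the clause alone would not recover their SAEs.
- Non-serious events are collected only to the last visit. Adding ET-only patients to every follow-up TEAE denominator would add people who can contribute no non-serious events and would dilute the rates.
- SAP 3.2 starts follow-up on the treatment-end date itself, so the Week 16 or ET visit might literally count as a follow-up visit. SAP 6.4 starts its follow-up windows one day later, and protocol 10.4.4.1 starts follow-up after the Week 16 visit date. At best this makes the set ambiguous, and it does not help a sponsor-stopped patient with neither visit.

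These points narrow the concern and its remedy. They do not explain why a serious event the protocol requires to be reported should have no period table.

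**Conclusion.** The concern holds in a limited form. Under SAP 3.2 a death or SAE with onset after the treatment-period end date, in a patient with no later visit, is left out of both period tables. It would still appear in listings, and it belongs in the overall-period analysis that SAP 3.2 promises. That safeguard is weakened because SAP 5.8.1 does not name the overall period and because no end date is set for a patient without an EOS visit.

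The number of affected patients and events is not in the documents and may be zero. If there is one, it moves an arm's follow-up SAE rate by about 3.8 percentage points, assuming 26 treated patients per arm. All analyses are descriptive, so no test is affected. What is at stake is whether the by-arm tables of serious events are complete. The sponsor should make the change before database lock.

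This assumes that follow-up visits are those after the treatment-period end date, as SAP 6.4 implies, and that SAEs after early termination reach the database under protocol 9.4.2. A second provision in 9.4.2 narrows reporting beyond 30 days after the EOS or ET visit to fatal and drug-related SAEs. The first 30 days, and all deaths the investigator learns of, are reportable on either reading.

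**What to change.** 1. **SAP 3.2, follow-up SAE and death tables:** drop the visit condition. Use all SAF patients alive at the treatment-period end date, including those with only an ET visit, and count every event with later onset reported by any route.
2. **SAP 3.2, period end:** where there is no EOS visit, end the follow-up and overall periods at death or, for SAEs, 140 days after the last dose, in line with protocol 9.4.2.
3. **SAP 5.8.1:** name the overall study period on the full SAF for TEAE, SAE and death tables, as protocol 10.4.4.1 does for TEAEs.
4. **Keep the visit condition** for by-visit laboratory, vital-sign and ECG summaries and for non-serious follow-up TEAEs, or show observation time beside the denominator. SAP 5.6.2 already derives an observation period up to the last visit.
5. **SAP 1.2.4:** list the visit condition, in whatever form remains, as a departure from the protocol.

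**Cost:** edits to three SAP sections, a subset flag and a period-end rule in programming. No new data are needed. The downside is that the SAE and death denominator will include some patients with short or passive follow-up, which a footnote should state.

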3.3. Pharmacokinetic Analysis Set (PKAS)

The PK analysis set includes all randomized patients who received any study drug and who had at least one non-missing study drug concentration result following the first dose of study drug. Patients will be analyzed according to the treatment actually received.

3.4. The Immunogenicity Analysis Set

The ADA analysis set (AAS) includes all patients who received any study drug and had at least 1 non-missing ADA result in REGN3500 ADA assay, after the first dose of the study drug. Patients will be analyzed according to the treatment actually received.

4. ANALYSIS VARIABLES

4.1. Demographic and Baseline Characteristics

The baseline value is defined as the last available value prior to the first dose of study drug, unless otherwise specified. For patients randomized but not treated, the baseline value is the last available value up to randomization.

The following demographic and baseline characteristics variables will be summarized:

- Demographic variables: Age at screening with grouping (year; ≥ 18 -<40, ≥ 40 -<65, ≥ 65 -<75), sex, ethnicity with grouping (Hispanic or Latino, Not-Hispanic or Latino), race with grouping (White, Black, Asian, Other), region, country, baseline weight with grouping (kg, <70; ≥ 70 -<100, ≥ 100), height (m), and BMI (kg/m^2 ; <15, ≥ 15 -<25, ≥ 25 -<30, ≥ 30), patients with inadequate response to topicals (Yes/No) with the reasons for patients who are “No” for inadequate response to topicals.
- Baseline characteristics: Duration of AD disease with grouping (year; < median duration, \geq median duration), Pruritus numerical rating scale (NRS) for maximum or average itch intensity, Pruritus categorical scale, Investigator’s Global Assessment (IGA) score, Eczema Area and Severity Index (EASI) score, SCORing Atopic Dermatitis (SCORAD) score, Body Surface Area (BSA) Involvement of Atopic Dermatitis, Patient Oriented Eczema Measure (POEM), Dermatology Life Quality Index (DLQI), Global Individual Signs Score (GISS), Hospital Anxiety and Depression Scale (HADS), history of eye/conjunctival disorder (such as conjunctivitis, blepharitis or keratitis), and findings of ophthalmological exam at Baseline.

4.2. Medical History

Medical history will be coded to a Preferred Term (PT), High Level Term (HLT) and associated primary System Organ Class (SOC) according to the latest available version of the Medical Dictionary for Regulatory Activities (MedDRA) at the coding CRO. Information on conditions related to AD includes diagnosis of AD and AD treatment history, asthma, allergic conjunctivitis, allergic rhinitis, chronic rhinosinusitis, nasal polyps, eosinophilic esophagitis, food allergy, hives and other allergies due to medications, animals, plants, mold, etc. will be collected.

4.3. Prior / Concomitant Medication

Medications/Procedures will be recorded from the day of informed consent until the end of study (EOS) visit. Medications will be coded to the ATC level 2 (therapeutic main group) and ATC level 4 (chemical/therapeutic subgroup), according to the latest available version of WHO Drug Dictionary at the coding CRO. Patients will be counted once in all ATC categories linked to the medication.

Procedures will be coded to a Preferred Term (PT), High Level Term (HLT) and associated primary System Organ Class (SOC) according to the latest available version of MedDRA at the coding CRO.

Prior medications/procedures: medications taken or procedures performed prior to the first dose of study drug.

Concomitant medications/procedures: medications taken or procedures performed following the first dose of study drug through the EOS visit.

The prior systemic corticosteroid, immunosuppressant, phototherapy use and concomitant topical steroid eye drops or cyclosporine eye drops will be adjudicated by the clinical study director and the adjudication procedure will be documented before database lock.

4.4. Rescue Medication/or Prohibited Medication During Study

Prohibited concomitant medications: Treatment with the following concomitant medications is prohibited during the study:

- Treatment with a live (attenuated) vaccine
- Treatment with an investigational drug (other than REGN3500)
- Treatment with immunomodulating biologics
- Treatment with systemic nonsteroidal immunosuppressant (may be used as rescue)
- Treatment with systemic corticosteroids (may be used as rescue)
- Treatment with TCS or TCI (may be used as rescue in which study drug will not be discontinued)
- Treatment with topical crisaborole (may be used as rescue in which study drug will not be discontinued)
- Initiation of treatment of AD with prescription moisturizers

Prohibited concomitant procedures: The following concomitant procedures are prohibited during study participation:

- Major elective surgical procedures
- Phototherapy (UVA, UVB, nbUVB, high dose UVA and PUVA)
- Tanning in a bed/booth

Rescue treatments (both medications and procedures): If medically necessary (ie, to control intolerable AD symptoms), study patients may receive rescue treatment for AD at the discretion of the investigator. If a patient receives rescue treatment with systemic corticosteroids or non-steroidal systemic immunosuppressive drugs, study treatment will be permanently discontinued immediately. If rescue treatment consists of topical medications, the patient can continue study drug treatment.

Unless permanently discontinued from the study or discontinued from study due to sponsor's decision of stopping the study, all patients will complete the scheduled study visits and assessments whether or not they complete study treatment and whether or not they receive rescue treatment for AD. Investigators should make every attempt to conduct efficacy and safety assessments (eg, disease severity scores, safety labs) immediately before administering any rescue treatment. An unscheduled visit may be used for this purpose, if necessary.

Blinded adjudication of rescue treatments will be implemented before database locks by considering the type of medication or procedure, indication, timing, frequency and the potential impact of the use of the prohibited medication or procedure. The rescue treatments will be adjudicated by the clinical study director and the adjudication procedure will be documented.

4.5. Efficacy Variable

All endpoints will be collected at time points according to [Table 1](#).

4.5.1. Primary Efficacy Variable

The primary efficacy variable in the study is the percent change in EASI score from baseline to week 16.

Eczema Area and Severity Index (EASI)

The EASI is a validated measure used in clinical practice and clinical trials to assess the severity and extent of AD ([Hanifin, 2001](#)). The EASI score calculation is based upon the Physician's Assessment of Individual Signs [erythema (E), induration/papulation (I), excoriation (X), and lichenification (L)], where each sign is scored as 0 = Absent, 1 = Mild, 2 = Moderate, or 3 = Severe, and also upon the Area Score [based on the % (BSA) affected] where 0 = 0% BSA, 1 = 1-9% BSA, 2 = 10-29% BSA, 3 = 30-49% BSA, 4 = 50-69% BSA, 5 = 70-89% BSA, 6 = 90-100% BSA.

For each of major section of the body (head, upper extremities, trunk and lower extremities), EASI score = (E+I+X+L) x Area Score. The total EASI score is the weighted total of the section EASI using the weights. For patients of age ≥ 8 years, the weights are 10% = head, 20% = upper extremities, 30% = trunk, 40% = lower extremities. For patients of age < 8 years, the weights are 20% = head, 20% = upper extremities, 30% = trunk, 30% = lower extremities. The minimum possible EASI score is 0 and the maximum possible EASI score is 72 where a higher score indicates increased extent and severity of atopic dermatitis. The EASI score of each sign (E, I, X and L) can be calculated in a similar way, for example, the EASI score of erythema = weighted sum of E x Area Score at each section.

